Participant or appropriate medical decision maker may provide written notice to formally withdraw from study. In the event of formal withdrawal from study, any specimen collected and stored as part of study will be discarded. However, other clinical specimen may still be collected as part of providing routine SOC. The intervention arm of this study involves 2 treatments of TPE. If participant declines TPE but consents to continued data collection, we will crossover participant to the SOC comparator arm of this study. If participant undergoes at least 1 session of TPE but consents to continued data collection, they will remain in the intervention arm of this study.

15. Risks to Participants

All participants in this study are critically ill with COVID-19 and require ICU admission. Such patients experience frequent complications and events that can cause deterioration in function of any and all vital organs. Specific risks associated with this research protocol are limited to possible complications related to apheresis/transfusion procedure that the TPE group will receive, as opposed to the SOC group. The following are known complications associated with all apheresis/transfusions regardless of indication:

- Hypotension
- Hypocalcemia
- Citrate Toxicity
- ACE Inhibitor Reactions
- Transfusion-associated circulatory overload (TACO)
- Transfusion-related acute lung injury (TRALI)
- Transfusion-associated dyspnea (TAD)
- Allergic reaction (where severity can range from mild to life threatening and rarely death)
- Hypotensive transfusion reaction
- Febrile non-hemolytic transfusion reaction (FNHTR)
- Acute hemolytic transfusion reaction (AHTR)
- Delayed hemolytic transfusion reaction (DHTR)
- Transfusion-transmitted infection (TTI)

While we do not anticipate that the relative risks will fundamentally differ, these risks are actively disclosed to patients as part of the routine consent process. Minor/mild

reactions (hypotension, hypocalcemia, allergic) are not uncommon, whereas others occur in <1% of procedures (citrate toxicity), or are extremely rare (hemolytic transfusion reactions). TPE is performed by trained nurses who are well-versed in recognizing these known complications and following protocols that include mitigation strategies for potential side effects.

No potential risks are foreseen to be associated with any of the testing, as it will be conducted on samples from the unit collected as part of routine care.

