16. Potential Benefits to Participants

Study participants may directly benefit from preventing/mitigating thromboembolic complications, and improvement in clinical outcome (organ function, enhanced probability of survival, shortened time to recovery).

17. Data Management and Confidentiality

Data Analysis

Sample size and power considerations: The primary efficacy outcome for the two parallel group clinical trial is plasma viscosity. Sample size and power considerations for the primary outcome, plasma viscosity, were based on longitudinal data (before and after PLEX treatment) from 7 patients (mean = 3.4 and 1.6 centipoise before and after PLEX treatment; standard deviation = 0.69 and 0.15 centipoise before and after PLEX treatment). The primary goal of the trial is to compare the change across time in the PLEX arm to the change across time in the standard of care arm. Group sample sizes of 10 in the PLEX arm and 10 subjects in the standard of care arm achieve 93% power to detect a difference in mean change between treatment groups of 1.0 centipoise in a design with pre/post measurements. These power calculations for plasma viscosity change assume a 1.5 centipoise improvement (decline) on average between baseline and after PLEX treatment and 0.5 centipoise improvement on average in the standard of care group. This sample size calculation assumes the estimated standard deviation of the differences of 0.61 centipoise and the correlation between paired plasma viscosity measurements on the same subject of 0.60. The significance level (alpha) is 0.05 using a two-sided, two-sample t-test. If the estimated standard deviation of the differences is as high as 0.75, the power will be 80%. All plasma viscosity power calculations were done with PASS 15 Power Analysis and Sample Size Software (2017). NCSS, LLC. Kaysville, Utah, USA, ncss.com/software/pass.

Statistical Analysis Plan: The primary analyses of the data will be performed according to subjects' original treatment assignment (i.e., intention-to- treat analyses) regardless of compliance to treatment and the inclusion of all data from all subjects randomized in the final analysis. The primary endpoint in this intent-to-treat, parallel-group trial will be mean plasma viscosity. A repeated-measures analysis of plasma viscosity will be performed with a means model via the SAS MIXED Procedure (version 9.4; SAS Institute, Cary, NC), providing separate

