estimates of mean plasma viscosity by time on study (before and after treatment) and treatment group.

The model will include three predictors [treatment arm, time on study (categorical) and the statistical interaction between treatment arm and time on study]. A compound-symmetric variance-covariance form in repeated measurements will be assumed for plasma viscosity and robust estimates of the standard errors of parameters will be used to perform statistical tests construct 95% confidence intervals¹⁷. The model-based means are unbiased with unbalanced and missing data, as long as the missing data are non-informative (missing at random, MAR). A P-value ≤ 0.05 will be considered statistically significant for the main effects (treatment and time on study) and for the treatment by time on study interaction effect from the repeated-measures analysis. **The statistical test for interaction between time on study and treatment will be the overall hypothesis test to determine whether plasma viscosity in the two study groups changed in significantly different ways during follow-up (i.e., different temporal patterns over time).** If mean plasma viscosity in the two treatment groups is consistently different or similar over time (i.e., no statistical interaction) then the main effect test for treatment will be used as the primary hypothesis test to compare the 2 treatment groups. The primary study results from this model will be the mean plasma viscosity and 95% confidence interval for the PLEX group, the mean plasma viscosity and 95% confidence interval for the standard of care group and the mean difference and 95% confidence interval. If a significant interaction is detected, then t-tests will be used to compare the differences between the model-based treatment means at each time point and to compare differences over time within each treatment arm. Specific statistical tests will be done within the framework of the mixed effects linear model. All statistical tests will be 2-sided and unadjusted for multiple comparisons. Secondary outcomes for additional laboratory parameters (fibrinogen, d-dimer, CRP, IL-6, and immunoglobulin levels) will be analyzed using the same plan described for plasma viscosity.

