This trial will provide important estimates of variability (within-subject and between-subject standard deviation) for plasma viscosity. The estimates of variability will be valuable to power future clinical trials since these variability estimates are essential components for sample size calculations. Due to the small sample sizes, results from these studies will also focus on the magnitude of the differences for each outcome, consistency of findings and clinical significance.

Duration of ICU stay, total time to hospital discharge and time on respiratory support will be compared by treatment group with the Wilcoxon rank-sum test. The assessment for a difference in hospital mortality and bleeding/thromboembolic complications by treatment group will be a two-sided exact chi-square test.

Study Ability to Detect Uncommon Safety Events

Adverse Events (AE) means any untoward medical occurrence associated with the use of an intervention in humans, whether or not considered intervention-related (21 CFR 312.32 (a)). An adverse event (AE) or suspected adverse reaction is considered "serious" if, in the view of either the investigator or sponsor, it results in any of the following outcomes: death, a life-threatening

adverse event, inpatient hospitalization or prolongation of existing hospitalization, a persistent or significant incapacity or substantial disruption of the ability to conduct normal life functions, or a congenital anomaly/birth defect. The following guidelines will be used to describe severity.

- **Mild** – Events require minimal or no treatment and do not interfere with the participant's daily activities.
- **Moderate** – Events result in a low level of inconvenience or concern with the therapeutic measures. Moderate events may cause some interference with functioning.
- **Severe** – Events interrupt a participant's usual daily activity and may require systemic drug therapy or other treatment. Severe events are usually potentially life-threatening or incapacitating. Of note, the term "severe" does not necessarily equate to "serious".]

All adverse events (AEs) must have their relationship to study intervention assessed by the clinician who examines and evaluates the participant based on temporal relationship and his/her clinical judgment. The degree of certainty about causality will be graded using the categories below.

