- **Related** – The AE is known to occur with the study intervention, there is a reasonable possibility that the study intervention caused the AE, or there is a temporal relationship between the study intervention and event. Reasonable possibility means that there is evidence to suggest a causal relationship between the study intervention and the AE.
- **Not Related** – There is not a reasonable possibility that the administration of the study intervention caused the event, there is no temporal relationship between the study intervention and event onset, or an alternate etiology has been established.

All participants in this study are critically ill with COVID-19 and require ICU admission. Such patients experience frequent complications and events that can cause deterioration in function of any and all vital organs. Any medical condition that is present at the time that the participant is screened will be considered as baseline and not reported as an AE. However, if the study participant's condition appears to deteriorate in response to the procedure it will be recorded as an AE.

The table below addresses safety using adverse event probabilities based on the targeted enrollment of 10 patients in each treatment group. The table provides the binomial probabilities of observing 0, 1+, or 2 or more occurrences of an AE during follow-up.

Adverse Event Probabilities for n=10 PLEX patients or n=10 standard of care patients

Event Rate (AE)	Probability [0 / 10 Events]	Probability [1+ / 10 Events]	Probability [2+ / 10 Events]
5%	0.60	0.40	0.09
10%	0.35	0.65	0.26
15%	0.20	0.80	0.46

Thus, we can be **80%** sure of observing at least one episode of a rare AE if the true rate of an AE is 15%.

Adverse Events and Laboratory Toxicities: Each adverse event and each laboratory toxicity will be counted only once per participant as the most severe level reported during follow-up. Tabular summaries of the number of participants reporting each AE, for both treatment-related and unrelated AEs as well as just treatment related AEs, respectively will be reported. Adverse events and grade III or higher laboratory toxicities observed during follow-up will be reported by treatment group.

Data Storage

1. All data will be kept on encrypted and password-secure Emory University Hospital computer systems, encrypted devices that are Emory IT vetted, or secure Emory servers, such as Trusted storage, with only the investigators listed having access to review the data.

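### Section 14 moves TPE-arm patients who decline TPE into the SOC arm, and Section 17 does not expressly rule this out for the clinical secondary outcomes

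*Combined protocol and SAP*

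**What the plan says.** Section 14 (Withdrawal of Participants) has two rules for patients randomised to TPE who allow data collection to continue. For those who have no TPE: "If participant declines TPE but consents to continued data collection, we will crossover participant to the SOC comparator arm of this study". For those with at least one session: "they will remain in the intervention arm of this study".

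Section 17 (Statistical Analysis Plan) bases the primary analyses on original assignment, "regardless of compliance to treatment and the inclusion of all data from all subjects randomized in the final analysis", and calls the study an intent-to-treat trial when it names the primary endpoint. The secondary laboratory outcomes "will be analyzed using the same plan described for plasma viscosity", so they inherit that basis.

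The clinical secondary outcomes have their own paragraph. ICU stay, time to discharge and "time on respiratory support will be compared by treatment group with the Wilcoxon rank-sum test". For the binary outcomes: "The assessment for a difference in hospital mortality and bleeding/thromboembolic complications by treatment group will be a two-sided exact chi-square test". In the adverse event text, events and higher-grade "laboratory toxicities observed during follow-up will be reported by treatment group". Neither place says whether the group is the one randomised or the one under Section 14.

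**The concern.** Read together, the two Section 14 rules assign patients by what they received. A decision to decline comes after randomisation, is made by a critically ill patient or a surrogate, and may be related to prognosis. No sham procedure or masking is described. If the Section 14 arm were used for mortality, thrombosis or length of stay, a selected group would leave the TPE arm and join SOC, and the comparison would no longer be protected by randomisation.

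With 10 patients per arm, one or two moves change the denominators noticeably. The plan also says that, because the samples are small, "results from these studies will also focus on the magnitude of the differences for each outcome". A biased estimate therefore matters even where no test is significant.

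**Working it through.** **The plan's own figure.** No figure in the plan is disputed. The sample size behind this check does reproduce: 10 per arm, a difference of 1.0 cp and an SD of 0.61 give a noncentrality of 1.0/(0.61 × √(2/10)) = 3.67 on 18 df and a power of 93.4%, against the stated 93%.

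**Which outcomes have a stated basis.**
- Viscosity: original assignment, stated.
- Fibrinogen, d-dimer, CRP, IL-6, immunoglobulins: original assignment, by reference.
- Hospital mortality, bleeding/thromboembolism, ICU stay, time to discharge, time on respiratory support: treatment group, basis not stated.
- Adverse event tables: treatment group, population not stated.

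**Bias in a risk difference if Section 14 is followed.** From the documents: 10 per arm. Assumed: no true TPE effect; k patients per arm of the type who would decline (k = 1, 2, 3); and a risk gap of d points between decliner and acceptor types. The TPE arm keeps 10 − k acceptors. SOC then holds 10 + k patients, 2k of them decliner types. The spurious difference is

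d × 2k/(10 + k).

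| Gap d | k = 1 | k = 2 | k = 3 |
|---|---|---|---|
| 10 points | 1.8 | 3.3 | 4.6 |
| 20 points | 3.6 | 6.7 | 9.2 |
| 30 points | 5.5 | 10.0 | 13.8 |

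For example, take acceptor risk 40%, decliner risk 60% and k = 2. The TPE arm shows 40%. SOC shows (8 × 40 + 4 × 60)/12 = 46.7%, a difference of 6.7 points. As randomised, both arms show (8 × 40 + 2 × 60)/10 = 44%. The sign reverses if decliners have the better prognosis.

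**False-positive rate of the exact test.** Full enumeration, with acceptor risk 30% to 70%, decline probability 10% to 30% and no TPE effect:
- 20-point gap, either direction: 2.0% to 4.2% under the Section 14 allocation, 1.0% to 1.3% as randomised.
- No gap, so no bias is possible: 1.9% to 2.3% under the Section 14 allocation, 1.2% to 1.3% as randomised.

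Part of the rise therefore comes from unequal arm sizes making a discrete test less conservative. At acceptor risk 40%, decliner risk 60% and 10% declining, the rate is 2.08%, against 1.99% with no gap. Every value is below 5%.

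**False-positive rate of the rank-sum test.** Simulation of 40,000 trials per setting, normal outcome (for example log-days), no TPE effect, decline probability 10%, 20%, 30%:
- decliner types shifted by 0.5 SD: 4.8%, 5.7%, 6.3%;
- shifted by 1 SD: 5.5%, 8.3%, 11.2%;
- as randomised: 4.2% to 4.5% throughout.

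**The case against.** The strongest reply is that the plan already settles this. Section 17 opens with original assignment and speaks of an intent-to-treat trial. It uses the term treatment group within the viscosity analysis that is plainly intention-to-treat, so the same term in the later paragraph of the same plan should mean the same thing. Section 14, on this view, is a withdrawal section about consent, specimens and follow-up. It mentions no analysis, and its crossover is ordinary non-compliance.

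Most of that stands, and it makes as-randomised the likelier reading. It does not close the matter. The two intention-to-treat statements are attached to the primary analyses and the primary endpoint. Section 14 is the only text specifically about decliners, it speaks of comparator and intervention arms for patients kept for data collection, and nothing confines it to care. An analyst could follow it and still be within the protocol.

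Four stronger inferences are tempting and not supported:
- That the primary viscosity result is compromised. Its basis is expressly original assignment.
- That the exact tests would produce many false positives. They stay below 5%, and part of the rise is not bias.
- That adverse events must be tabulated as randomised. They are tabulated by group, and grouping by treatment received is acceptable if declared. The gap is only that the population is not named.
- That decliners alone lack a starting point for the 3, 7, 14 and 28-day outcomes. Section 4 counts these from the last exchange, which is undefined for the whole SOC arm. A clock for decliners alone would not solve this. It is a separate issue that needs one anchor for both arms.

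**Conclusion.** The Section 14 rule conflicts with the intention-to-treat principle of Section 17. The conflict is left open in practice for the five clinical outcomes compared by treatment group, and the adverse event tables lack a named population. The documents do not show that the investigators intend an as-treated analysis.

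If Section 14 were followed, the main harm would be a biased estimate: 3.6 to 9.2 points for 1 to 3 decliner types per arm at a 20-point gap, in either direction. The rank-sum outcomes could also exceed the nominal 5%, but the largest rate shown needs 30% declining and a 1 SD difference. The decline rate, risk gap and shift are all assumptions, and with one decliner type per arm the effect is modest. Confidence is medium: the conflict is in the text, but its size is unknown. It is worth settling before data are seen because the correction is so small.

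**What to change.** Replace the Section 14 sentence on decliners with: *Participants who decline TPE but agree to continued data collection are followed on SOC, remain in their randomised arm for all between-arm comparisons of efficacy and clinical outcomes, and are recorded as not having received TPE.*

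Add to Section 17: *Intention-to-treat also applies to the clinical secondary outcomes.*

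For the adverse event tables, state the population. One option is as randomised, with TPE-related events also summarised among patients with at least one session. The other is by treatment received, if so declared.

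No new data are needed, and primary power does not change because the primary analysis already follows original assignment. The cost is dilution. With decliners of equal prognosis, a true 20-point effect in treated patients appears as 20 × (10 − k)/10 = 18, 16 or 14 points for k = 1, 2 or 3. A 30% TPE-related event rate in treated patients would likewise appear as 27%, 24% or 21% of the randomised arm, which is the reason to keep a treated-patient safety summary if the tables are as randomised.

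### The compound-symmetric covariance conflicts with the plan's own SDs of 0.69 cp before and 0.15 cp after TPE, so the variability estimates drawn from it and the unqualified MAR statement do not hold as written

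*Combined protocol and SAP*

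**What the plan says.** All the relevant text is in Section 17 (Data Management and Confidentiality).

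- The Statistical Analysis Plan fits a repeated-measures means model with arm, time and their interaction. On the covariance it says: "A compound-symmetric variance-covariance form in repeated measurements will be assumed for plasma viscosity". Robust standard errors are planned. No other structure is named, and nothing says whether the covariance may differ by arm.
- On missing data it says: "The model-based means are unbiased with unbalanced and missing data, as long as the missing data are non-informative (missing at random, MAR". No condition on the covariance is attached.
- The power paragraph takes its inputs from seven treated patients: "standard deviation = 0.69 and 0.15 centipoise before and after PLEX treatment". It then assumes a "standard deviation of the differences of 0.61 centipoise and the correlation between paired plasma viscosity measurements on the same subject of 0.60".
- A later paragraph presents variability as a product of the trial: "This trial will provide important estimates of variability (within-subject and between-subject standard deviation) for plasma viscosity". It adds that these estimates are needed to size future trials.

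**The concern.** Compound symmetry has two parameters: one variance, shared by all time points, and one covariance. If no grouping by arm is specified, both are also pooled over arms. The plan's TPE figures imply a variance ratio of 0.69²/0.15² = 0.4761/0.0225, about 21. A spread that shrinks after treatment in one arm only is also what the trial hypothesis predicts, since TPE is expected to normalise viscosity.

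Two things are at stake. One is the variability estimates, because SDs pooled over unlike cells may describe none of them. The other is the protection claimed against missing post-treatment samples. A likelihood model in effect predicts a missing post value from the baseline value, and with the wrong covariance it uses the wrong slope. The same analysis plan is applied to fibrinogen, d-dimer, CRP, IL-6 and immunoglobulins.

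**Working it through.** **1. The plan's own figures.** SD of differences = √(0.69² + 0.15² − 2 × 0.60 × 0.69 × 0.15) = √(0.4761 + 0.0225 − 0.1242) = √0.3744 = 0.612 (stated 0.61). A two-sided two-sample t-test with 10 per arm, a difference of 1.0 cp and 18 df has power 93.4% at SD 0.61 (stated 93%) and 80.5% at SD 0.75 (stated 80%). The figures reproduce, and they rest on unequal SDs.

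**2. What compound symmetry returns with complete pairs.** The common variance V is the mean of the cell variances. The common covariance C is the mean of the arm covariances. Between-subject SD = √C, within-subject SD = √(V − C), implied SD of change = √(2(V − C)).

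- TPE arm alone: V = (0.4761 + 0.0225)/2 = 0.2493 and C = 0.60 × 0.69 × 0.15 = 0.0621. SD is 0.50 at both times (plan: 0.69 and 0.15), correlation 0.25 (plan: 0.60), SD of change 0.612 (correct).
- Pooled with SOC at SD 0.69 both times, correlation 0.60 (assumed; the documents give no SOC SD): V = (3 × 0.4761 + 0.0225)/4 = 0.3627 and C = (0.0621 + 0.2857)/2 = 0.1739. SD 0.60, correlation 0.48, between-subject SD 0.42, within-subject SD 0.43, SD of change 0.615 (true values 0.612 TPE, 0.617 SOC).
- Baseline and SOC SD 0.35, post-TPE SD 0.15, correlation 0.60 (assumed): V = (3 × 0.1225 + 0.0225)/4 = 0.0975. SD 0.31, still twice 0.15.

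The value 0.35 is the SD of a uniform spread over the 2.3-3.5 cp entry range: 1.2/√12 = 0.35.

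Recovery of the SD of change depends on SOC resembling TPE in this respect. With an SOC correlation of 0.3 or 0.8 the pooled value is 0.72 or 0.53, while the TPE value stays 0.61.

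**3. Bias when post values are missing according to baseline.** In each arm, bias of the post mean = (true slope − model slope) × (mean baseline of patients with a post value − mean baseline of all). The true TPE slope is 0.60 × 0.15/0.69 = 0.13. The model slope is its fitted correlation: 0.48 with complete data, and higher once high baselines lose their post value.

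Example, SD 0.69, highest fifth of baselines lost in both arms: the remaining mean baseline is 0.35 SD low, that is −0.35 × 0.69 = −0.242 cp. The fitted slope is 0.587. TPE bias = (0.130 − 0.587) × (−0.242) = +0.110. SOC bias = (0.600 − 0.587) × (−0.242) = −0.003. The effect is biased by +0.11 cp, toward no effect.

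Large-sample fits, with post values missing by a logistic function of baseline (log-odds slope 1 or 2 per SD) or with the highest baselines lost, in both arms or in TPE only:

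| Assumed missing | SD 0.69 | SD 0.35 |
|---|---|---|
| 0% | 0 | 0 |
| 10% | 0.02-0.06 cp | 0.01-0.02 cp |
| 20% | 0.05-0.11 cp | 0.02-0.04 cp |

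At the planned 10 per arm, with SD 0.69, 20% missing and the steeper logistic pattern, simulation gives +0.09 cp under compound symmetry. A separate unstructured covariance per arm gives +0.004 (simulation error 0.005).

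**4. Scale.** Planned standard error of the effect = 0.61 × √(2/10) = 0.27 cp. In the 0.35 scenario the SD of change is about 0.30, so the like-for-like standard error is 0.30 × √(2/10) = 0.13 cp. Either way the bias is at most about 0.4 of a standard error (0.11/0.27 = 0.41; 0.04/0.13 = 0.31).

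**The case against.** The strongest reply is that the trial's main result is safe. With complete pairs the means, and hence the interaction, do not depend on the covariance form. The planned robust standard errors protect the tests from a wrong form, within the limits of 20 patients. The SD on which this trial is powered is recovered. All of this stands.

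The 21-fold variance ratio also cannot be carried over to the trial. Four of the seven pilot patients had viscosity above 3.5 cp (Section 3), and such patients are excluded (Section 10). Values confined to 2.3-3.5 cp cannot have an SD above 0.60, although entry through fibrinogen can widen the spread. This stands too, and it is why the 0.35 scenario is shown. The conflict shrinks but does not vanish.

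The plan does not say that variability will be reported only from the compound-symmetric components, nor that the covariance is common to both arms. Both are natural readings, since within- and between-subject SDs are what such a model yields and no grouping is named, but they remain inferences.

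Finally, missing data may be few. The post sample is due by Day 3 or 4, and patients expected to die within 24 hours are excluded. The documents give no missing-data rate, so 10-20% is an assumption.

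**Conclusion.** The point holds in a limited form. The assumed structure contradicts the SDs that the plan itself used, and two statements need correcting. The between-subject SD, the pre/post correlation and any time- or arm-specific SD from this model would mislead: SD 0.60 and correlation 0.48 in one scenario, SD 0.31 in the other, against a post-TPE SD of 0.15. The MAR statement is true only with a correctly specified covariance, and robust standard errors do not repair a biased mean. The size of that bias is about 0.04 to 0.10 cp with SD 0.69 (0.02 to 0.11 over every pattern tried) and about 0.01 to 0.04 cp with SD 0.35, always toward no effect. This rests on assumed SOC SDs, a correlation of 0.60 and assumed missingness.

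A reader might go further in three ways that the documents do not support:

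- That a later trial sized from these estimates must be wrongly sized. One sized on the SD of change, as this trial was, would not be if SOC is similar. Mis-sizing by a stated multiple needs a baseline-adjusted design and SOC SDs that the documents do not give.
- That any missing post sample biases the effect. Missingness must be related to baseline viscosity; values missing completely at random cause no bias.
- That the primary comparison is invalid. With complete pairs it is not.

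**What to change.** In the Statistical Analysis Plan of Section 17:

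- Replace compound symmetry with an unstructured 2 × 2 covariance fitted separately by arm (TYPE=UN with GROUP=arm in the MIXED procedure). State that Kenward-Roger inference replaces the robust standard errors in this model.
- Define the variability estimates to be reported as the SD at each time, the SD of change and the pre/post correlation, each by arm.
- Qualify the MAR sentence: the means are unbiased under MAR provided that the covariance is correctly specified.
- Carry the same change to the secondary laboratory parameters, which follow the same plan.

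The cost is a few lines and no new data. With complete pairs the estimated effect is identical. The drawback is six covariance parameters instead of two, each estimated from about 10 patients, so they will be imprecise and should be reported with confidence intervals. If six prove unstable, reporting the observed SDs by arm and time needs no change of model and still mends the variability estimates, but it leaves the MAR sentence in need of its condition.

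### The main-effect fallback gives the primary claim a second unadjusted test, averages in the pre-treatment value, and raises the false-positive rate from 5% to about 7–10%

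*Combined protocol and SAP*

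**What the plan says.** The Statistical Analysis Plan in Section 17 fits a repeated-measures model with arm, time and their interaction. The model gives "estimates of mean plasma viscosity by time on study (before and after treatment) and treatment group", so time has two levels. The interaction is called the overall hypothesis test. If the arms show a consistent difference or a consistent similarity over time, described as no interaction, "then the main effect test for treatment will be used as the primary hypothesis test to compare the 2 treatment groups".

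A P-value of 0.05 or less "will be considered statistically significant for the main effects (treatment and time on study) and for the treatment by time on study interaction effect". The plan adds: "All statistical tests will be 2-sided and unadjusted for multiple comparisons". On variance it states: "A compound-symmetric variance-covariance form in repeated measurements will be assumed for plasma viscosity and robust estimates of the standard errors of parameters".

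The results sentence begins "The primary study results from this model will be the mean plasma viscosity and 95% confidence interval for the PLEX group". It goes on to the same summary for standard of care and a mean difference, without saying at which time that difference is taken or whether it is a difference in change. After a significant interaction, "If a significant interaction is detected, then t-tests will be used to compare the differences between the model-based treatment means at each time point". The additional laboratory outcomes "will be analyzed using the same plan described for plasma viscosity".

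Elsewhere the target is the change. Section 4 defines the primary endpoint as the difference between the pre-TPE value and the value after the second TPE. The sample-size paragraph of Section 17 gives the comparison of changes between arms as the trial's goal and powers the trial for a 1.0 cp difference in mean change. The analysis plan, however, names mean plasma viscosity as the primary endpoint.

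**The concern.** Two things are wrong with the fallback.

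First, it is a second route to a positive primary result. Each route is taken at the full 0.05, and no section splits alpha between them.

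Second, it tests a different quantity. With two time levels, the treatment main effect is half the pre-treatment difference plus half the post-treatment difference. The first half is chance under randomisation. If the arms really differ by the same amount at both times, which is one of the patterns said to trigger the fallback, they already differed before treatment. That is a baseline imbalance, not an effect of plasma exchange.

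At stake is the meaning of a positive primary result. With 10 patients per arm, chance imbalances can be large, and the rule allows one to be reported as the outcome of the primary hypothesis test.

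**Working it through.** **Inputs (Section 17, sample-size paragraph).** 10 per arm; two-sided alpha 0.05; difference in mean change 1.0 cp; SD of the differences 0.61 cp (0.75 as sensitivity); pre/post correlation 0.60; pilot SDs 0.69 cp before and 0.15 cp after treatment. Degrees of freedom are 18 and the critical t is 2.101.

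**The plan's own figures.** For the two-sample t-test on change, the noncentrality is 1.0 / (SD × √(2/10)).
- SD 0.61: noncentrality 3.67, power 93.4% (stated 93%).
- SD 0.75: noncentrality 2.98, power 80.5% (stated 80%).
- The pilot SDs give √(0.69² + 0.15² − 2 × 0.60 × 0.69 × 0.15) = 0.612, in line with the stated 0.61.

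The power statement therefore describes the interaction contrast.

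**The two tests.** With complete data, the interaction is the arm difference in D = post − pre. The main effect is the arm difference in A = (pre + post)/2. The covariance of D and A is (SD_post² − SD_pre²)/2.

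**False-positive rate with equal SDs.** The covariance is zero, so under normality the two tests are independent. The two-step rate is 1 − 0.95² = 0.0975, whatever the common SD and correlation. Simulation with SD 0.61/√(2 × (1 − 0.60)) = 0.682 agrees (0.097–0.098 in runs of 2,000,000 trials).

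**False-positive rate with the pilot SDs in both arms.** D and A have correlation −0.94, so the second test adds less.

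| No treatment effect, 18 df | Interaction alone | Two-step rule |
|---|---|---|
| Ordinary SE, equal SDs | 5.0% | 9.75% |
| Ordinary SE, SDs 0.69/0.15 | 5.0% | 6.7% |
| Uncorrected robust SE, equal SDs | 6.2% | 11.9% |
| Uncorrected robust SE, SDs 0.69/0.15 | 6.2% | 8.2% |

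With SDs 0.69/0.15 and ordinary t-tests, the two-step rate is 7.1% at correlation 0 and 6.3% at correlation 0.8. Assumed SD pairs in between (0.35/0.15, 0.69/0.35, 0.35/0.25, 0.69/0.50) give 8.1% to 9.4%.

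The robust rows rest on an assumption, because the plan states neither a small-sample correction nor degrees of freedom. With complete data the uncorrected robust SE is the ordinary SE × √(9/10). A single test then has P(|t₁₈| > 2.101 × √0.9) = 0.0616, and two independent tests have 1 − (1 − 0.0616)² = 0.119.

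**What the extra false positives look like.** Among null trials significant only through the fallback, 56–57% already had a pre-treatment arm difference significant at 0.05. The mean absolute pre-treatment difference in those trials was about 0.6 cp.

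**Under the planned effect.** With a 1.0 cp difference in change and no expected baseline difference, the main effect has expectation (0 + 1.0)/2 = 0.5 cp.

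| Planned effect, ordinary t-tests | Interaction | Main effect alone | Either test |
|---|---|---|---|
| Equal SDs 0.682 | 93% | 41% | 96% |
| SDs 0.69/0.15 | 93% | 76% | almost 100% |

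The fallback is reached in about 7% of trials under the planned effect and in 95% when there is no effect.

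**The case against.** The strongest reply is that chance baseline difference is not peculiar to the main effect. Post minus pre contains the same difference, with weight −1 instead of ½. With the pilot SDs, the baseline difference correlates −0.98 with the interaction contrast and +0.99 with the main effect; with equal SDs the figures are −0.45 and +0.89. Randomisation makes the baseline difference zero on average, so the main-effect test alone holds 5%. This is correct. The inflation comes from the second unadjusted test, and the baseline term matters for a separate reason: the averaged quantity is not the endpoint and halves the effect sought.

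The 6.7% can also be challenged. The 0.15 cp is an SD measured after plasma exchange, and applying it to both arms when treatment does nothing is artificial. Section 3 reports that four of the seven pilot patients were above 3.5 cp, a level that Section 10 excludes. SDs closer to each other move the rate towards 9.75%, so this does not help the plan.

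Part of the robust-SE rise (5.0% to 6.2%) is a separate issue that deleting the fallback would not cure. The mean difference in the results sentence might be meant as a difference in change, but the text does not say so.

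Finally, this is a 20-patient Phase 1 trial. Section 17 says results will also be judged on magnitude, consistency and clinical significance, and means are reported by arm and time. A reader could therefore spot a baseline-driven result. That softens the consequence but leaves in place the rule that decides the primary test.

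**Conclusion.** The concern holds and must be fixed. As written, the plan has two unadjusted primary tests in sequence, and the second concerns a quantity that is neither the endpoint nor the powered difference. The false-positive rate is 6.7% to 9.75% with ordinary t-tests, against 5.0% for the interaction alone. It would be about 8% to 12% if robust standard errors are used uncorrected with 18 degrees of freedom.

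These rates assume normal, complete data, the usual equal weighting of the two times in the main effect, and that significance on either primary test counts as a positive result, which is how the plan reads. The harm is greatest when the true effect is absent or small. No rate is given for the laboratory outcomes, because Section 4 calls them repeated without giving the number of time points.

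**What to change.** - Delete the sentence that makes the treatment main effect the primary test when there is no interaction.
- Name the between-arm difference in change (the interaction contrast) as the only primary test, at two-sided alpha 0.05, and report it with its 95% confidence interval as the primary result.
- Align the sentence that names mean plasma viscosity as the primary endpoint with Section 4.
- Keep the t-tests planned after a significant interaction, labelled as secondary follow-up.
- Remove the fallback for the laboratory outcomes as well. If any of them has more than two time points, state the contrast of interest.

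A baseline-adjusted comparison of the post-treatment value would also be a single test at 5%. The change contrast is proposed because the endpoint, goal and power calculation already use it.

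The cost is analysis-plan wording only, to be settled before the outcome data are analysed. The sample size and the 93% and 80% power statements stand. What is given up is the chance that either test is significant under the planned effect: 96% to almost 100%, against 93% for the interaction alone. Those extra positive results concern the averaged difference, not the change.
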